5.3 Pharmacokinetics analysis procedure

5.3.1 *Blood sample collection procedure*

The collection of blood samples will be done through a heparinized catheter inserted into the superficial vein of the volunteer's forearm. After each blood collection, the catheter will be washed with 1 mL of sodium heparin solution (5000 IU/mL in 0.90% sterile NaCl). Samples will be collected at the following times: immediately before the application of PSI, and 15, 30, 60, 180, and 360 minutes after the application of PSI.

In total, 6 samples of approximately 4.9 mL (5 mL tube) of blood will be collected from each participant for the BZ371A dosage. Thus, approximately 29.40 mL of blood will be used for the pharmacokinetic study. In addition, adding to the 40 mL for laboratory tests before and after the application of PSI, a total of approximately 69.40 mL of blood will be collected during the study period for each participant.

The absolute real time of each blood sample collection should be recorded in the Clinical Record Forms (CRF) using a 24-hour clock. The absolute real time of the IP application should also be recorded,

so that the actual time interval between the application of IP and the respective collections can be computed. Any loss of sample collection should also be recorded. The collected samples should allow for the unequivocal identification of the study, research subject (identification code), collection period, and time.

In this study, yellow tubes with clot activator and gel separator will be used for blood sample collection. These two components cause the blood to clot more quickly, and after clotting, the gel performs the physical separation between the cellular and liquid (serum) portions. After collection, the samples should be kept in an ice bath at $4^{\circ}\text{C} \pm 2^{\circ}\text{C}$ from collection until centrifugation.

5.3.2 *Blood sample processing and storage*

The blood samples will be centrifuged at approximately 3,000 rpm for 10 minutes at 4°C ($\pm 2^{\circ}\text{C}$). Immediately after centrifugation, a minimum of 1.2 mL of serum from each sample will be collected and aliquoted into 3 transparent Eppendorf LoBind tubes with a maximum capacity of 1.5 mL. The minimum volume of serum collected will be 1.2 mL and will be divided equally among the 3 tubes (e.g., if exactly 1.2 mL of serum is collected, each Eppendorf LoBind tube will have approximately 400 μL of volume). The remaining serum will be transferred to another cryogenic tube as a reserve sample.

Lo Bind Eppendorf tubes will be stored in polypropylene boxes labeled with the study name, study code, period, and subject number. These boxes will be stored at a temperature $< -70^{\circ}\text{C} \pm 5^{\circ}\text{C}$ in a specific freezer for the storage of biological samples, at the research center.

The period between sample collection, centrifugation, and storage in the freezer should not exceed 30 minutes.

5.3.3 *Blood sample transportation and analysis*

The transportation of samples from the storage unit to the analytical unit will be carried out in thermal boxes containing dry ice and a digital thermometer where the maximum and minimum temperatures reached are recorded.

The company *Unidade de Integração Farmacologia e Gastroenterologia* (UNIFAG) is the analytical company that will quantify BZ371A and its fragments in the samples.

If the peptide or its fragments are detected, the following pharmacokinetic parameters must be determined: maximum concentration (C_{max}), half-life (t_{1/2}), area under the curve (AUC), clearance (CL), volume of distribution (V_d).

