3. STUDY PLAN

3.1 General study design

Open-label study, conducted at a single center, with the aim of being the first human trial with the new BZ371A formulation in order to guide future clinical studies such as to understand safety, tolerability, and systemic bioavailability of the peptide topically applied.

The study will comprise only one group, consisting of 6 men and 6 women.

The formulation will be administered in a single dose, topically, followed by medical and laboratory analyses for safety assessment, and blood collections for pharmacokinetic analysis.

The concentration of BZ371A and its fragments in the blood will be measured by an appropriate analytical method, developed for this purpose and previously validated. The collected blood will be

analyzed by the company *Unidade Integrada de Farmacologia e Gastroenterologia* (UNIFAG), the same company that validated the analytical method, and will not be stored or used for any other purpose.

The visits and procedures are illustrated in the table below:

CHART 1. VISITS AND BZ371CLI003 STUDY PROCEDURES

| Visit | V-1 | V0 | V1 |
|--|-----------|-----------------------|-----------------|
| Day | D-1 | D0 | D7 |
| Interval | -7 a 0 | 0 | +2 a -2 |
| Visit Name | Screening | PK | Safety revision |
| ICF | X | | |
| Demographic data | X | | |
| Medical history | X | X | |
| Physical exam | X | | X |
| Genitalia exam | X | X / X ^(*) | X |
| Anthropometric data | X | | |
| Vital Signs | X | X / X ^(**) | X |
| Concomitant medication | X | X | X |
| Blood collection for laboratory analysis | X | X ^(*) | |
| Urine collection | X | X ^(*) | |
| Electrocardiogram | X | X ^(*) | X |
| Eligibility | X | X | |
| Blood sample collection for PK | | X | |
| BZ371A application | | X | |
| AE collection | | X | X |
| Next visit scheduling | X | X | |
| Study dismissal | | | X |

^{*}: after 360 minutes after IP application

^{**}: after IP application at 30, 60, 180 and 360

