In order to be completed, physical examination must be performed at V-1 and V1 to capture diseases and AEs, respectively. The assessment includes a general inspection (skin, oropharynx, and appendages), and cardiovascular, pulmonary, digestive, musculoskeletal, peripheral, and neurological exams.

Physical examination of the male or female genitalia must be performed at all visits: at V-1, for eligibility assessment; at V0, before and 360 minutes after IP administration, for AE assessment; and at V1, for AE assessment.

5.2.4 *Blood and urine sample collection*

In order to evaluate the systemic safety of the PSI, blood and urine will be collected before (at V-1) and after the application of the IP (at V0 at the 360-minute time point), for analysis of the following laboratory tests: (i) complete blood count, including platelets; (ii) coagulogram, including PT and PTT; (iii) biochemistry, including glucose, sodium, potassium, urea, creatinine, chloride, total calcium, phosphorus, total and fractionated proteins (albumin and globulin), TGO, or AST, TGP or ALT, alkaline phosphatase, gamma GT, total cholesterol, HDL cholesterol, triglycerides, pH; (iv) urinalysis.

In addition, blood will be collected from women during the V-1 visit for the β -HCG test and confirmation of absence of pregnancy, allowing the participant to be included in the study.

Approximately 20 ml of blood will be collected per evaluation (V-1 and V0), totaling 40 ml of blood for laboratory tests.

Any difference between the baseline and post-application of the IP should be evaluated by the examiner and, if clinically significant, should be noted as an AE.

5.2.5 *Electrocardiogram*

In order to evaluate the cardiac safety of PSI, an ECG examination will be performed at all visits. At V0, it should be performed 360 minutes after the administration of PSI, with a window of +/- 30 minutes. At V-1 and V1, the cardiac evaluation can be performed concurrently with the clinical evaluation.

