The standard 12-lead ECG examination will be performed and an analytical report must be provided descriptively and/or conclusively in accordance with the Guidelines of the Brazilian Society of Cardiology on Electrocardiographic Analysis and Reports. The interpretation of the tracing should be performed by a physician and clinically significant abnormalities (and/or those related to the current health condition) should be recorded as relevant medical history and/or current conditions during the screening visit, which should be analyzed by the Investigator physician as a risk or not for inclusion in the study. Other clinically significant abnormalities found after the administration of IP should be reported and evaluated by the Investigator physician as EA. All ECG reports should be kept as part of the study documentation.

5.2.6 *Participants food*

In order to maintain standardization of blood collection for pharmacokinetics, unbalanced feeding will follow the same pattern for all participants.

- Fluids: water intake is free during the study.
- Food: At visit V-1, participants must fast for at least 6 hours and a maximum of 10 hours before blood collection for laboratory tests. After this collection, participants can eat without restrictions. At visit V0, participants can receive a light breakfast before starting blood collection for pharmacokinetics and after 2 hours of IP application.

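### High-strength heparin flushes precede the only scheduled post-dose coagulation panel, so a changed 360-minute aPTT could not be reliably attributed to BZ371A or cleared of it

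*Combined protocol and SAP*

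**What the plan says.** **Flush.** PK blood is taken through a heparinized forearm catheter (Section 5.3.1), with this rule: "After each blood collection, the catheter will be washed with 1 mL of sodium heparin solution (5000 IU/mL in 0.90% sterile NaCl"). The draws are "immediately before the application of PSI, and 15, 30, 60, 180, and 360 minutes after the application of PSI".

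**Safety laboratory tests.** Section 2.2 lists PT and aPTT among the safety outcomes, and safety is a primary goal in Section 2.1. Section 5.2.4 gives the timing: "blood and urine will be collected before (at V-1) and after the application of the IP (at V0 at the 360-minute time point"). Chart 1 in Section 3.1 agrees. Its row reads "Blood collection for laboratory analysis | X | X", with V1 left empty, and the V0 mark carries the footnote "after 360 minutes after IP application". Section 5.2.4 also says how the results are used: "Any difference between the baseline and post-application of the IP should be evaluated by the examiner", and a clinically significant difference becomes an AE.

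**Comparator.** "The study will comprise only one group, consisting of 6 men and 6 women" (Section 3.1). No laboratory panel is scheduled on the dosing day before application.

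**Food.** Section 5.2.6 requires a 6 to 10 hour fast before the V-1 laboratory draw. At V0 it permits a light breakfast before PK sampling and food again 2 hours after application. It adds that "unbalanced feeding will follow the same pattern for all participants".

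**Causality.** Section 7.6 and its Chart 5 classify each AE by timing, other causes and known effect. Table 1 in Section 7.2 lists the expected effects; no coagulation change is among them.

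**The concern.** Heparin is an anticoagulant, and aPTT is the listed test most directly exposed to it. The protocol gives heparin repeatedly, at high strength, in the six hours before the one post-dose coagulation measurement. The baseline (V-1) is taken on a different visit, before any flush. The V-1 to V0 difference therefore contains whatever the product does plus whatever the flushes do. All 12 participants follow the same rule, so nothing within the study separates the two.

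This matters for a primary objective in healthy volunteers who expect no benefit (Section 8.5.1). They would also receive heparin that the PK sampling may not need. The flush after the 360-minute draw in particular serves no later scheduled PK sample.

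**Working it through.** **1. Counts, checked against the plan's own figures.** PK blood: 6 x 4.9 mL = 29.4 mL. Laboratory blood: 2 x 20 mL = 40 mL. Total: 69.4 mL. All three agree with Sections 5.2.4 and 5.3.1, which confirms six PK draws and only two laboratory panels, one of them post-dose.

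**2. Nominal heparin before the panel.** One flush is 1 mL x 5000 IU/mL = 5000 IU. The draws before 360 minutes are pre-dose, 15, 30, 60 and 180 minutes.
- Five flushes: 5 x 5000 = 25,000 IU.
- Six flushes, if the 360-minute PK draw and its flush come first: 6 x 5000 = 30,000 IU.

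Section 5.2.4 puts the panel at the 360-minute time point, while the Chart 1 footnote says after it. Either order is open. These totals are upper bounds on what enters the circulation, because part of each flush may stay in the catheter or be withdrawn at the next draw.

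**3. What might remain at 360 minutes (assumed inputs).** The documents give neither the fraction *f* of each flush that reaches the circulation nor a half-life *h*. Assume *f* = 10% to 100%, *h* = 30 to 120 minutes and first-order decline:

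Residual = sum over t = 0, 15, 30, 60, 180 of 5000 x f x 0.5^((360 - t)/h).

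For example, with f = 1 and h = 60: 78 + 93 + 110 + 156 + 625 = about 1,063 IU (summed before rounding). A sixth flush directly before the panel adds 5000 x f.

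| f | h (min) | Five flushes (IU) | Sixth directly before (IU) |
|---|---|---|---|
| 0.1 | 30 | 8.8 | 509 |
| 0.1 | 60 | 106 | 606 |
| 0.1 | 120 | 470 | 970 |
| 0.5 | 30 | 44 | 2,544 |
| 0.5 | 60 | 531 | 3,031 |
| 0.5 | 120 | 2,351 | 4,851 |
| 1 | 30 | 88 | 5,088 |
| 1 | 60 | 1,063 | 6,063 |
| 1 | 120 | 4,702 | 9,702 |

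The range, about 9 to 9,700 IU, is too wide to predict an aPTT result. It shows only that neither a negligible nor a large residual can be excluded from the text.

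**4. With a weaker lock (assumed strength).** At 10 to 100 IU/mL, five 1 mL flushes total 50 to 500 IU, which is 25,000/500 = 50 to 25,000/50 = 500 times less than planned. Saline gives zero.

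**5. How Chart 5 would treat a changed aPTT.** The change follows dosing, so take timing as yes. It is not in Table 1, so take known effect as no.
- Other cause no: Possible, counted as related.
- Other cause yes (heparin accepted as a strong alternative): Improbable, which corresponds to the Unlikely category and is counted as not related.

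The classification turns on whether heparin is accepted as the cause, and the design supplies no data to decide that. The error can go either way.

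**6. Food.** The panel is at 360 minutes and food is allowed from 120 minutes, so 360 - 120 = 240 minutes. Time since food is then 4 hours or less if the later food is taken, against 6 to 10 hours at V-1. If only the pre-dose breakfast is eaten, it is at least 6 hours, which meets the V-1 minimum.

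**The case against.** The strongest reply is that no effect on aPTT is shown. Half-life and systemic fraction are assumptions, the residual spans three orders of magnitude, and it is not converted to an aPTT change. That stands. A reader might infer from the 25,000 IU that aPTT will be prolonged, or that this dose is delivered to each volunteer. The documents support neither.

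A reader might also infer that the safety panel is drawn through the heparinized catheter, or after a sixth flush. The catheter text sits under the PK procedure, Section 5.2.4 does not mention a catheter, and one draw followed by one flush at 360 minutes would comply. Route and order are simply unstated. A separate venipuncture would remove carry-over but not circulating heparin, so the five earlier flushes remain an issue.

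Nor is the whole panel compromised. Chart 4 relies on biochemistry and urinalysis for tubulopathy and unknown effects. Creatinine, urea, electrolytes and urinalysis are not challenged here. A normal 360-minute aPTT would still be largely reassuring; only a shortening could be masked.

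It can be said that the investigator will allow for heparin, that Section 7.6 offers a non-evaluable category, that Section 9 describes every AE, and that unscheduled visits (Section 3.1) permit a repeat test. All true, so no event is lost. But these rules report the uncertainty without resolving it, and no repeat panel is required. It would also be wrong to conclude that the danger is only a false alarm: Chart 5 can equally dismiss a real effect.

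On food, the reply mostly succeeds. Eating is optional, the pattern is common to all and known, and the examiner can allow for it. A reading that glucose and triglycerides are uninterpretable goes too far.

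**Conclusion.** The point holds for aPTT. Followed as written, the flush rule places nominally 25,000 IU of heparin, or 30,000 IU in the less favourable draw order, before the only scheduled post-dose coagulation panel. There is no control group and no same-day pre-dose panel to separate its effect. A changed 360-minute aPTT could therefore be wrongly ascribed to BZ371A or wrongly classed as not related.

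The flush counts and nominal doses come straight from the documents. The only outside premise is the general one that heparin can prolong aPTT; how far it would do so here is unknown. The residuals above illustrate that uncertainty and are not estimates.

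This is a cheap improvement worth making before first dosing, not a defect that invalidates the safety assessment. The fed-versus-fasted mismatch for glucose and triglycerides is minor and secondary.

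**What to change.** **Section 5.3.1.** Verify that 5000 IU/mL is the intended strength before anyone is dosed. Replace it with saline or a low-dose heparin lock. Omit the flush after the final 360-minute draw.

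**Section 5.2.4.** State that the 360-minute safety panel is drawn before any 360-minute flush and without carry-over from heparin in the catheter, for example by separate venipuncture.

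**Section 5.2.6 (minor).** Allow no food between the pre-dose breakfast and the 360-minute draw. That gives at least 6 hours, matching the V-1 minimum.

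**Cost.** Protocol wording and a different flush solution, with possibly a slightly higher risk of catheter clotting. If separate venipuncture is chosen, it is one per participant, 12 in all, with no added blood because the 20 mL panel is already in the 69.4 mL total. The food rule means at least 6 hours without eating at V0.

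Keeping the present rules and declaring that the 360-minute aPTT, glucose or triglycerides will not be judged is not a good substitute. It gives up their only scheduled post-dose comparison and conflicts with Section 5.2.4, which requires differences from baseline to be evaluated.

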2.2 Endpoints

For safety and tolerability analysis of BZ371A, the following outcomes were considered:

- Report of adverse events (AE);
- Local physical examination of the genital area;
- Vital signs, including systemic blood pressure (BP) and heart rate (HR);
- Electrocardiogram (ECG);
- Laboratory tests, including (i) complete blood count, including platelets; (ii) coagulation profile, including prothrombin time (PT) and activated partial thromboplastin time (aPTT); (iii) biochemistry, including glucose, sodium, potassium, urea, creatinine, chloride, total calcium, phosphorus, total protein and fraction (albumin and globulin), aspartate aminotransferase (AST), alanine aminotransferase (ALT), alkaline phosphatase, gamma-glutamyl transferase (GGT), total cholesterol, HDL cholesterol, triglycerides, and pH; (iv) urinalysis for abnormal elements and sediments (EAS).

For pharmacokinetics analysis of BZ371A, the following outcomes will be considered:

- Detection of BZ371A and its fragments in the blood at the following timepoints: pre-dose, 15, 30, 60, 180, and 360 minutes;
- If detected, determination of the pharmacokinetic parameters: maximum concentration (Cmax), half-life (t_{1/2}), area under the curve (AUC), clearance (CL), volume of distribution (Vd).

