4. STUDY POPULATION

4.1 Participant eligibility

The study group will consist of 12 healthy adults, 6 males and 6 females, with no restrictions on ethnicity, social class, or group. Participants should not have injuries that could compromise the study results, nor diseases that could compromise their safety.

4.1.1 *Inclusion Criteria*

1. Men or women above 18 years of age;
2. Body mass index (BMI) > 19 and < 28.5 kg/m²;

- 3. Ability to understand the informed consent form.

4.1.2 *Exclusion Criteria*

- 1. Women who are menstruating or pregnant (confirmed by a positive β -HCG test);
- 2. Diseases that interfere with the absorption, distribution, and excretion of drugs, such as a history or presence of liver or kidney diseases;
- 3. Presence of genital lesions or active sexually transmitted diseases (STDs) (such as herpes, gonorrhea, candidiasis, HPV, among others) that impair the analysis of local adverse effects on the genitalia;
- 4. Presence of lesions that may compromise the study results, or diseases that may compromise their safety;
- 5. Use of topical medications in the genital region that may interfere with the evaluation of the experimental medication;
- 6. History of symptomatic hypotension, or diseases that increase the risk of symptomatic hypotension, such as patients with heart disease (including a history of angina and/or heart failure) and kidney disease;
- 7. Findings on ECG and/or laboratory tests that, at the investigator's discretion, are considered significant and pose a risk to the research participant's participation or may interfere with the study's analyses;
- 8. Blood pressure (BP) outside the considered safe limits: systolic BP less than 90 mmHg or greater than 140 mmHg; or diastolic BP less than 60 mmHg or greater than 90 mmHg, except in situations such as "white coat syndrome."
- 9. Any disease or condition or physical finding that the investigator considers significant and that increases the risk of the research participant's participation or may interfere with the results.

The research participant will be eligible if they meet all inclusion criteria and no exclusion criteria.

4.2 *Screening and recruitment*

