8.8 Protocol deviations and violations

The procedures described in the protocol must be followed in full, taking appropriate measures to prevent protocol deviations. However, in the event of any complications, it is the responsibility of the researchers to analyze and evaluate the situation, as well as take appropriate actions accordingly.

Protocol deviation is defined as any failure to comply with the procedures or requirements defined in the version of the protocol approved by the Ethics Committee (EC) without significant implications for the study integrity, data quality, or participant rights and safety. On the other hand, protocol violation refers to a deviation from the protocol that may affect data quality, compromise the integrity of the study, or impact the safety or rights of the participants. In general, a significant deviation from the protocol is considered a protocol violation, while a minor deviation is considered a protocol deviation.

Any deviation from the plan outlined in this protocol must be described, justified, and included in the Final Report.

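### As written, section 5.3.1 flushes 5,000 IU of heparin after each PK draw, up to 25,000 IU by the 180-minute draw, with no dilution, maximum or discard step stated

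*Combined protocol and SAP*

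**What the plan says.** Section 5.3.1 (Blood sample collection procedure) takes PK blood through a heparinized forearm catheter. The draws are "immediately before the application of PSI, and 15, 30, 60, 180, and 360 minutes after the application of PSI". The flush instruction is "After each blood collection, the catheter will be washed with 1 mL of sodium heparin solution (5000 IU/mL in 0.90% sterile NaCl"). It gives volume, strength, diluent and frequency. It gives no further dilution, no limit on the total, and no instruction to withdraw the lock or discard blood before a sample. Section 8.8 adds: "The procedures described in the protocol must be followed in full".

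Section 2.2 lists among the safety outcomes a "coagulation profile, including prothrombin time (PT) and activated partial thromboplastin time (aPTT"). Section 5.2.4 fixes the timing: "blood and urine will be collected before (at V-1) and after the application of the IP (at V0 at the 360-minute time point"). Chart 1 schedules no laboratory blood at V1. On design, section 3.1 states: "The study will comprise only one group, consisting of 6 men and 6 women".

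Section 8.5.2 names bruising as the only risk of blood collection, and section 8.5.1 expects no individual benefit.

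**The concern.** The sentence in 5.3.1 can be carried out exactly as printed, and 8.8 tells staff to do so. Carried out that way, it puts a repeated anticoagulant into a line that stays in a healthy volunteer's vein for six hours. Four of the flushes fall at or before the 60-minute draw. The sampling does not need this if saline or a weak heparin solution keeps the line open.

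Two things are at stake. The first is participant safety: an exposure with no stated ceiling that the risk section does not mention. The second is the reading of one named safety outcome. PTT is measured once after dosing, after several heparin flushes, and no untreated group has the same flushes. If it is prolonged, the product and the flush are competing explanations.

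**Working it through.** **Inputs.** From 5.3.1: 1 mL per flush, 5000 IU/mL, six draws at 0 (pre-dose), 15, 30, 60, 180 and 360 minutes, about 4.9 mL per PK sample. From 5.2.4: about 20 mL of laboratory blood at each of V-1 and V0.

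**The plan's own blood volume.** PK: 6 × 4.9 = 29.40 mL. Laboratory: 2 × 20 = 40 mL. Total: 29.40 + 40 = 69.40 mL, which matches 5.3.1. The remainder is 69.40 − 29.40 − 40 = 0 mL, so the budget contains no discard.

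**Heparin flushed, as written.** Per flush: 1 mL × 5000 IU/mL = 5,000 IU. Cumulative amount = number of flushes × 5,000 IU.

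| Draw (min) | Flushed before this draw (IU) | Flushed after this draw's wash (IU) |
|---|---|---|
| 0 | 0 | 5,000 |
| 15 | 5,000 | 10,000 |
| 30 | 10,000 | 15,000 |
| 60 | 15,000 | 20,000 |
| 180 | 20,000 | 25,000 |
| 360 | 25,000 | 30,000, only if this draw is also flushed |

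The relevant figure is 25,000 IU, the amount already flushed when the 360-minute blood is due. The last flush serves no later scheduled PK sample. The table counts only flushes after PK draws. Any heparin already in the catheter at insertion is not quantified in the plan and is not included.

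**If 5000 IU/mL is a stock strength.** The plan gives no diluted strength. At an assumed 10–100 IU/mL, five flushes give 5 × 1 × 10 = 50 IU to 5 × 1 × 100 = 500 IU. Six give 60–600 IU. The range only illustrates what the other reading would mean.

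**What would catch or limit it.** The exclusion criteria in 4.1.2 are general: "Presence of lesions that may compromise the study results, or diseases that may compromise their safety" (criterion 4), "Findings on ECG and/or laboratory tests that, at the investigator's discretion, are considered significant" (criterion 7), and any finding the investigator thinks raises risk (criterion 9). They act on entry, not on the flush. PT and PTT are scheduled at V-1 and at 360 minutes, with no coagulation test between and none planned afterwards. The 360-minute sample comes 360 − 180 = 180 minutes after the fifth flush.

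**Effect on causality.** Under 5.2.4, a clinically significant change from baseline becomes an adverse event. Chart 5 in 7.6 then applies. For an effect that fits in time and is not known for the product, the rating is possible (counted as related) if no other cause is recognised, and improbable (counted as not related) if one is. The rating therefore turns on whether the assessor counts the flush as another cause. A flush with a real heparin effect could be missed as a cause, or could be used to explain away a product effect.

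**The case against.** The strongest reply is that harm is not shown. The plan says the catheter is washed. It gives no dead space and no share entering the circulation, so 25,000 IU is an amount flushed, not a dose received. The parenthesis may describe a stock to be diluted, and site SOPs (section 10) may govern the preparation. On that reading the fault is one of wording. All of this stands as a limit on size. It does not remove the point, because on its face the parenthesis gives the strength of the washing solution and 5.3.1 refers to no SOP for it.

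A reader might infer that a prolonged 360-minute PTT could not be attributed at all. The documents do not support that. Section 7.6 makes other causes one of its three causality criteria, each participant has a V-1 baseline, and 5.2.4 requires differences from it to be evaluated. The last scheduled flush before the sample is 180 minutes earlier, and 5.2.4 does not say whether laboratory blood comes through the catheter. Attribution is harder, not impossible.

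A reader might also infer that the PK serum samples are compromised. Carry-over into tubes drawn after a flush is possible, but the residual volume is not given, so nothing here rests on it.

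There are general safeguards: a unit equipped for Phase I work (3.2), vital signs at 30, 60, 180 and 360 minutes (5.2.2), unscheduled visits (3.1), withdrawal for signs of toxicity (8.6.2) and symptom follow-up (7.9). They are real, but none limits the flush.

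**Conclusion.** The point holds in this form. As written, 5.3.1 specifies 5,000 IU per flush and up to 25,000 IU flushed by the 180-minute draw for each of 12 participants, with no dilution, ceiling or discard stated and no mention in 8.5.2. Following it exposes healthy volunteers to avoidable anticoagulant and makes one named safety outcome harder to interpret.

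The conclusion assumes that the sentence is carried out literally, as 8.8 requires, and that the 360-minute laboratory blood is taken no later than any sixth flush. The figures are upper bounds on the amount flushed. The documents do not show that participants would receive these amounts systemically, nor that 30,000 IU is needed under the sampling schedule. If the sponsor confirms that 5000 IU/mL is a stock strength, the exposure concern largely falls away, and what remains is an unclear instruction without a discard step. Confidence is medium for that reason, but the matter should be settled before anyone is dosed.

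**What to change.** Before dosing, the sponsor and site pharmacist should confirm the intended flush and correct 5.3.1 as follows:

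- Use saline, or a low-strength heparin flush with its final concentration and a maximum total per participant stated.
- Omit the flush after the 360-minute draw.
- Require a small discard before each draw that follows a flush (15, 30, 60, 180 and 360 minutes), and add it to the stated blood total.
- Take the 360-minute coagulation sample after the discard, or by a route other than the heparinized line.
- Only if 5000 IU/mL is truly intended, add the bleeding risk to 8.5.2 and review the 360-minute PT and PTT before the participant leaves V0.

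Cost: pharmacy confirmation and one amendment with ethics committee approval under 8.7.1. A pure clarification before study start might qualify as a correction under 8.7.2, but the discard changes the blood volume, so an amendment is the safer route. At an assumed 1–2 mL before five draws, the extra blood is 5–10 mL, giving 69.40 + 5 = 74.40 mL to 69.40 + 10 = 79.40 mL per participant. A weaker flush may make line blockage more likely in the longer gaps (180 − 60 = 120 minutes and 360 − 180 = 180 minutes), which could mean a repeat venepuncture. Reviewing the coagulation result on the day, if that step applies, may lengthen the V0 stay.
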